5.3 Schematic diagram

An overall schematic diagram with successive panels for each body weight category (<30kg, ≥30kg to <50kg, and ≥50kg) is provided in [Figure 5-1](#). The schematic diagram for the Transition Period is provided in [Figure 5-2](#).

Figure 5–1: SP0969 overall schematic diagram

[figure not shown]
[figure not shown]

Figure 5-1: SP0969 overall schematic diagram

T=Telephone Contact; V=Visit

Note: LCM dosing is designated as "mg/kg/day" (oral solution) and "mg/day" (tablets), and matching placebo is shown as "placebo."

Note: The subject's body weight at Baseline (Visit 2) will be used to determine dose throughout the study.

^a The study week numbers provided are for subjects who complete the Maintenance Period and enter the Taper Period. The study week numbers provided do not apply to subjects who enter the Taper Period at other times. The highest possible dose for each week of taper for each body weight category is shown; complete dosing information for the Taper Period is provided in [Table 7-5](#). Taper of LCM may not be required for some subjects who discontinue study medication prematurely depending on the treatment option selected by the investigator in consultation with the subject and/or parent/legal representative. There will be a 30-day Safety Follow-Up Period (see [Table 5-3](#)) for subjects not entering EP0034.

^b Subjects who complete the Maintenance Period and plan to participate in the open-label extension study (EP0034) will participate in a 4-week blinded Transition Period with dosing as shown in [Figure 5-2](#).

Figure 5–2: SP0969 schematic diagram (Transition Period)

[figure not shown]
[figure not shown]

Figure 5-2: SP0969 schematic diagram (Transition Period)

TV=Transition Visit

Note: LCM dosing is designated as “mg/kg/day” (oral solution) and “mg/day” (tablets), and matching placebo is shown as “placebo.”

Note: The subject’s body weight at Baseline (Visit 2) will be used to determine dose throughout the study.

5.4 Rationale for study design and selection of dose

Epilepsy is a condition for which an improved benefit/risk ratio for medicinal products remains a challenge; this is especially true for pediatric patients. Based on the demonstrated efficacy and safety of LCM as adjunctive treatment in subjects with epilepsy ≥ 16 years of age with partial-onset seizures, and the experience with other AEDs in pediatric subjects, it is likely that LCM will be an efficacious and safe treatment in the pediatric population with partial-onset seizures.

SP0969 is a Phase 3 multicenter, double-blind, randomized, placebo-controlled, parallel-group study to investigate the efficacy and safety of LCM as adjunctive therapy in subjects with epilepsy ≥ 4 years to < 17 years of age with partial-onset seizures. A Phase 3 study (SP0967) investigating the use of LCM in subjects with epilepsy ≥ 1 month to < 4 years of age with partial-onset seizures is planned.

Based on the currently available LCM pediatric safety and PK data from SP847 and SP1047, as well as on information available in the medical literature, the dosing recommendations for SP0969 are as follows to achieve LCM plasma concentrations corresponding to the average steady-state LCM plasma concentration (C_{ss}) reached after a LCM 400mg/day dose administration in adult studies, which is approximately $8\mu\text{g/mL}$:

- A weight-based dosing scheme is recommended for the Maintenance Period:
 - Subjects $< 30\text{kg}$: LCM 8mg/kg/day to 12mg/kg/day
 - Subjects $\geq 30\text{kg}$ to $< 50\text{kg}$: LCM 6mg/kg/day to 8mg/kg/day
 - Subjects $\geq 50\text{kg}$: LCM 300mg/day to 400mg/day
- The LCM (or matching placebo) dose should otherwise remain fixed over the Maintenance Period.
- To provide dosing flexibility and optimize tolerability for each subject during titration, flexible study medication dosing to achieve a minimum target dose for entry into the Maintenance Period. The dosing flexibility during the Titration Period includes 4 key elements:
 - A Titration Period of 6 weeks to allow sufficient time to achieve the minimum target dose for entry into the Maintenance Period for subjects who require study medication dosing flexibility based on tolerability.
 - Allowing investigators to hold a subject's study medication dose constant at any time during the Titration Period and allowing for multiple holds if needed.
 - Allowing investigators to back titrate a subject's study medication dose by full-step or half-step increments, with asymmetric dosing as needed for tablets.
 - Allowing flexibility in the duration a subject must remain on a back-titrated study medication dose before a subsequent increase.

- Administration of oral solution by feeding tube is permitted for subjects who are unable to swallow the oral solution; however, they are not permitted to exceed the maximum dose of LCM 400mg/day.
- Dosing with oral solution is permitted for subjects weighing ≥ 50 kg who are unable or unwilling to swallow tablets.

6 SELECTION AND WITHDRAWAL OF SUBJECTS

6.1 Inclusion criteria

To be eligible to participate in this study, all of the following criteria must be met:

1. An Institutional Review Board (IRB)/Independent Ethics Committee (IEC) approved written Informed Consent form is signed and dated by the parent(s) or legal representative. The Informed Consent form or a specific Assent form, where required, will be signed and dated by minors.
2. Subject/legal representative is considered reliable and capable of adhering to the protocol (eg, able to understand and complete diaries), visit schedule, and medication intake according to the judgment of the investigator.
3. Subject is male or female from ≥ 4 years to < 17 years of age.
4. Subject has a diagnosis of epilepsy with partial-onset seizures. The results of ≥ 1 prior electroencephalogram (EEG) AND 1 prior magnetic resonance imaging/computerized tomography scan should be consistent with the above diagnosis.
5. Subject has been observed to have uncontrolled partial-onset seizures after an adequate course of treatment (in the opinion of the investigator) with ≥ 2 AEDs (concurrently or sequentially).
6. Subject must have been observed to have on average ≥ 2 partial-onset seizures per 28 days with seizure-free phase no longer than 21 days in the 8-week period prior to entry into the Baseline Period. During this study, subjects must have reported ≥ 2 partial-onset seizures during the 8-week prospective Baseline Period to be eligible for randomization at Visit 2. (Note: In the case of simple partial-onset seizures, only those seizures with motor signs will be counted towards meeting the inclusion criterion.)
7. Subject is on a stable dosage regimen of 1 to ≤ 3 AEDs. The daily dosage regimen of concomitant AED therapy must be kept constant for a period of ≥ 4 weeks prior to the Baseline Period.
8. Vagal nerve stimulation is allowed and will not be counted as a concomitant AED. The VNS device must be implanted for ≥ 6 months before Visit 1, and the device settings must be stable for ≥ 4 weeks before Visit 1 and be kept stable during the Baseline Period. Use of the VNS device magnet is allowed.

6.2 Exclusion criteria

Subjects are not permitted to enroll in the study if any of the following criteria is met:

1. Subject has previously participated in this study or subject has been assigned to LCM in a previous LCM study.
2. Subject has participated in another study of an investigational medicinal product (IMP) or a medical device within ≤ 2 months of Visit 1 or is currently participating in another study of an IMP or a medical device.
3. Subject has any medical or psychiatric condition that, in the opinion of the investigator, could jeopardize or would compromise the subject's ability to participate in this study.
4. Subject ≥ 6 years of age has a lifetime history of suicide attempt (including an actual attempt, interrupted attempt, or aborted attempt), or has suicidal ideation in the past 6 months as indicated by a positive response ("Yes") to either Question 4 or Question 5 of the Columbia-Suicide Severity Rating Scale (C-SSRS) at Screening.
5. Subject has a known hypersensitivity to any component of the IMP or has ever received LCM.
6. Female subject who is pregnant or nursing, and/or a female subject of childbearing potential who is not surgically sterile or does not practice 1 highly effective method of contraception (according to International Conference on Harmonisation [ICH] guidance defined as those that result in a failure rate of less than 1% per year when used consistently and correctly), unless sexually abstinent, for the duration of the study. Female subject of childbearing potential taking enzyme-inducing antiepileptic drugs (EI-AEDs: carbamazepine, phenytoin, barbiturates, primidone, topiramate, oxcarbazepine) who is not surgically sterile or does not practice 1 highly effective method of contraception according to the WHO recommendation (ie, depot medroxyprogesterone acetate, norethisterone enantate, intrauterine devices, combined injectables, and progestogen implants) with administration of EI-AEDs OR does not practice 2 combined methods of contraception (ie, combined hormonal contraception plus barrier method with spermicidal agent), unless sexually abstinent, for the duration of the study.
7. Subject has a medical condition that could be expected in the opinion of the investigator to interfere with drug absorption, distribution, metabolism, or excretion.
8. Subject has experienced febrile seizures exclusively. The occurrence of febrile seizures in addition to other unprovoked seizures is not exclusionary.
9. Subject is on a ketogenic or other specialized diet. If the subject was on a specialized diet in the past, they must be off the diet for ≥ 2 months prior to the Baseline Period.
10. Subject has an alanine aminotransferase (ALT), aspartate aminotransferase (AST), or total bilirubin level ≥ 2 times the upper limit of normal (ULN), or creatinine clearance less than 30mL/min.
11. Subject has a clinically relevant ECG abnormality, in the opinion of the investigator (eg, second or third degree heart block at rest or a corrected QT interval [QTc] greater than 450ms).

12. Subject has hemodynamically significant congenital heart disease.
13. Subject has an arrhythmic heart condition requiring medical therapy.
14. Subject has a known history of severe anaphylactic reaction or serious blood dyscrasias.
15. Subject has nonepileptic events that could be confused with seizures.
16. Subject has a current diagnosis of Lennox-Gastaut syndrome, primary generalized epilepsy, mixed seizure disorder (partial and primarily generalized seizures), or purely nocturnal seizures.
17. Subject has a history of convulsive status epilepticus ≤ 2 months prior to the Baseline Period.
18. Subject has been treated with vigabatrin and experienced any vision loss. Subjects who have received vigabatrin in the past must have documentation of an assessment for vision loss prior to study entry or documentation of why visual field testing cannot be performed.
19. Subject has been treated with felbamate and has experienced any serious toxicity issues (defined as liver failure, aplastic anemia) with this treatment. Subjects treated with felbamate for <12 months are excluded. Note: any subject who has been treated with felbamate for ≥ 12 months and has not experienced serious toxicity issues is eligible.
21. Subject has a medically documented history of alcohol or drug abuse.
22. Subject has a known cardiac sodium channelopathy, such as Brugada syndrome.
23. Subject has an acute or sub-acutely progressive central nervous system disease. Subject has epilepsy secondary to a progressing cerebral disease or any other progressively neurodegenerative disease (malignant brain tumor or Rasmussen Syndrome).

6.3 Withdrawal criteria

Subjects are free to withdraw from the study at any time, without prejudice to their continued care.

Subjects **must** be withdrawn from this study if any of the following events occur:

1. Subject experiences intolerable AEs, including clinically relevant abnormal laboratory findings that, in the opinion of the investigator, preclude further participation in the study.
2. The sponsor or a regulatory agency requests withdrawal of the subject.
3. Subject has QTc interval ≥ 500 ms that is confirmed by a cardiologist overread on any ECG.
4. Subject develops a second degree atrioventricular (AV) block while awake or develops a third degree AV block.
5. For subjects ≥ 6 years of age, subject has actual suicidal ideation since last visit as indicated by a positive response ("Yes") to either Question 4 or Question 5 of the C-SSRS. The subject should be referred immediately to a Mental Healthcare Professional and must be withdrawn from the study.

6. Subject is unwilling or unable to continue, or the parent/legal representative is unwilling or unable to allow the subject to continue in the study.
7. Investigator decides that withdrawal from further participation would be in the subject's best interest.
8. Subject experiences convulsive status epilepticus.
9. Subject uses rescue medication in excess of that permitted by the protocol.
10. In the case of liver function test (LFT) results of transaminases (AST, ALT, or both) $\geq 3x$ ULN to $< 5x$ ULN and total bilirubin $\geq 2x$ ULN or transaminases (AST, ALT, or both) $\geq 5x$ ULN, the study medication must be immediately discontinued and the subject withdrawn from the study. The LFTs will be repeated as soon as possible, and in no case > 1 week later.
11. Female subject who achieves menarche and does not practice contraception as provided in Exclusion Criteria 6 unless sexually abstinent. Subject becomes pregnant, as evidenced by a positive pregnancy test.
12. Subject needs any alteration in AED daily dose or VNS settings.

Participation in this study may be discontinued for any of the following reasons:

1. Subject has any clinically relevant change in medical or psychiatric condition (if in the opinion of the investigator, the change in condition warrants discontinuation from the study).
2. Subject requires a medication that is not permitted by the protocol.
3. Subject and/or delegated caregiver is noncompliant with study procedures or medication, in the opinion of the investigator.
4. Subject needs any alteration in AED dosing frequency.
5. Transaminases (AST, ALT, or both) $\geq 3x$ ULN to $< 5x$ ULN, in the presence of normal total bilirubin, will be repeated within a few days. If the repeat testing confirms the abnormality (ie, transaminases are $\geq 3x$ ULN to $< 5x$ ULN with normal bilirubin), then weekly monitoring of LFTs should continue until resolved (ie, $< 3x$ ULN or stable condition). The investigator is to decide whether or not to stop the study medication.

Investigators should attempt to obtain information on subjects, in the case of withdrawal or discontinuation. For subjects considered as lost to follow-up, the investigator should make every effort (≥ 1 phone call and 1 written message to the parent[s] or legal representative), and document his/her effort (date and summary of the phone call and copy of the written message in the source documents) to complete the final evaluation. All results of these evaluations and observations, together with a narrative description of the reason(s) for removing the subject, must be recorded in the source documents. The Case Report form (CRF) must document the primary reason for withdrawal or discontinuation.

Investigators should contact the Medical Monitor whenever possible to discuss the withdrawal of a subject in advance.

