11.9.8 Assessment of suicidality

Suicidality will be assessed by trained study personnel using the C-SSRS (Columbia University Medical Center, 2008). This scale will be used for Screening as well as to assess suicidal ideation and behavior that may occur during the study. The C-SSRS will be completed according to the tabular schedules of study procedures (Section 5.2). All subjects who are ≥ 6 years of age will complete the "Baseline/Screening" version of the C-SSRS at Visit 1 and will complete the "Since Last Visit" version at subsequent visits. If a subject becomes 6 years of age during the study, the "Already Enrolled" version of the C-SSRS should be used at the first visit at which the subject is 6 years of age and use the "Since Last Visit" version at subsequent visits.

The C-SSRS is not validated for subjects < 6 years of age and will not be used for this population. Subjects should be monitored for any changes in mood, ideas, or behavior for warning signs of depression. The investigator should be aware of common warning signs that might be a signal for risk of depression. For common signs and symptoms of depression in children younger than 6 years old, reference should be made to the current version of the Diagnostic and Statistical Manual of Mental Disorders. Parents and caregivers should also be advised accordingly and effort should be made at clinic visits to specifically assess potential depression.

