#### 10.4.8 Assessment of suicidality

Suicidality will be assessed using the Columbia-Suicide Severity Rating Scale (C-SSRS). The scale will be used for Screening as well as to assess suicide ideation and behavior that may occur during the study. All subjects who are  $\geq 6$  years of age will complete the Baseline/Screening version of the C-SSRS at Visit 1 and will complete the Since Last Visit version at subsequent visits. If a subject becomes 6 years of age during the study, the Already Enrolled version of the C-SSRS should be used at the first visit at which the subject is 6 years of age and use the Since Last Visit version at subsequent visits.

The C-SSRS is not validated for subjects  $< 6$  years of age and will not be used for this population. For those subjects, signs and symptoms of depression will be assessed at each visit.

The C-SSRS assessment is completed throughout the study from Visit 1 (entry to study) to Visit 8, and at ETV in case of early termination, and at unscheduled visits. The C-SSRS assessment is also completed during the Transition Period, Taper Period, and at the Safety Follow-Up Visit.

Subject data listings of the data for the C-SSRS will be provided. No summaries of the C-SSRS data are planned.

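### On-study suicidal behaviour without Question 4/5 ideation has no specific mandated withdrawal or referral, and the C-SSRS data get no by-arm count

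*Protocol*

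**What the plan says.** Protocol 6.2, Exclusion 4, applies to subjects aged 6 or over and has two limbs. The first is a "lifetime history of suicide attempt (including an actual attempt, interrupted attempt, or aborted attempt"). The second is ideation in the past 6 months, shown by a Yes to C-SSRS Question 4 or 5 at Screening.

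Protocol 6.3, mandatory withdrawal criterion 5, applies to the same age group when the "subject has actual suicidal ideation since last visit as indicated by a positive response" to Question 4 or 5. It continues: "The subject should be referred immediately to a Mental Healthcare Professional and must be withdrawn from the study". Neither the mandatory nor the discretionary list in 6.3 names a suicide attempt or other suicidal behaviour.

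Protocol 11.9.8 states the purpose of the instrument: "This scale will be used for Screening as well as to assess suicidal ideation and behavior that may occur during the study".

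SAP 10.4.8 provides subject listings and adds: "No summaries of the C-SSRS data are planned". Separately, SAP 10.2 tabulates adverse events by treatment group, including the other significant AEs of Appendix 12.2, which has a suicidality category.

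**The concern.** The plan treats behaviour and ideation as equally disqualifying at entry, then carries only ideation into the specific on-study rule. A subject whose C-SSRS records an attempt, or an interrupted or aborted attempt, without a Yes to Question 4 or 5 meets no criterion written for that situation, and the referral instruction does not reach that subject as worded. With about 149 planned sites (Protocol 5.1.2; about 155 in SAP 2.3), the same recorded event can be handled differently from site to site.

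The analysis has a parallel gap. Safety and tolerability are the secondary objective, and the SAP makes suicidality a category of significant events. Yet the one instrument that asks about it systematically, in both arms and on a fixed schedule, contributes no count by arm.

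**Working it through.** The plan gives no figure to reproduce, so this is a comparison of text plus a count of scheduled assessments.

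**1. Entry against on-study criteria.** Exclusion 4 has a behaviour limb (three types) and an ideation limb (Question 4 or 5). Criterion 5 has an ideation limb on the same two questions and no behaviour limb. Referral is written inside criterion 5, so it follows the ideation limb only. Protocol 11.9.8 confirms that behaviour is assessed on study.

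**2. What does apply to behaviour without a Yes to Question 4 or 5.**
- Criterion 1 (mandatory list): intolerable AEs, in the investigator's opinion.
- Criterion 2 (mandatory list): a request from the sponsor or a regulator. This does not rest on site judgement, but nothing ties it to suicidal behaviour.
- Criterion 7 (mandatory list): "Investigator decides that withdrawal from further participation would be in the" best interest of the subject. This is a judgement.
- Discretionary item 1: "Subject has any clinically relevant change in medical or psychiatric condition". This permits discontinuation and does not require it.
- AE and SAE reporting (Protocol 11.1.1, 11.2.2, 11.4): all AEs go on the CRF, and SAEs reach the sponsor within 24 hours. Protocol 11.1.7 gives a suicide attempt as an example of an AE or SAE, in the context of excess dosing. Suicidality is not among the AEs of special interest in 11.3, so immediate reporting depends on the investigator classifying the event as serious.
- Real-time triage by the medical monitor and Drug Safety, then the IDMC as appropriate (Protocol 13.7, SAP 4.3). The SAP links this to Appendix 12.2.

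Each of these governs reporting, review or judgement. None prescribes withdrawal or referral because suicidal behaviour was recorded. By contrast, other items on the mandatory list use explicit triggers: QTc of 500 ms or more, AV block, convulsive status epilepticus and liver test thresholds.

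**3. How much scale data goes uncounted.** From Protocol Table 5-1, the C-SSRS is scheduled at Visits 1 to 8. Visits 1 and 2 precede the first dose, which is taken at the end of Visit 2. Visits 3, 4, 5, 6, 7 and 8 give 6 Treatment Period assessments per completer aged 6 or over. Tables 5-2 and 5-3 bring the total to 8 + 4 = 12 for a completer who goes through Transition, and 8 + 1 + 1 = 10 for one with a Taper Visit and a Safety Follow-Up Visit.

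For comparison, the CBCL has 2 scheduled post-Baseline assessments in the Treatment Period (Visits 5 and 8) and the BRIEF/BRIEF-P has 1 (Visit 8). SAP 10.4.7 and 10.4.9 summarise both by treatment group.

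**4. What reaches a by-arm table.** SAP 10.2 tabulates all TEAEs, serious TEAEs and TEAEs leading to discontinuation by SOC and preferred term. It also tabulates the Appendix 12.2 events, which include 11 suicidality terms. All of these start from an event that a site reported as an AE. None is built from C-SSRS responses, and none uses the number of subjects assessed on the scale as its denominator.

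**The case against.** The strongest case on the other side has four parts.

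- **Entry and withdrawal criteria need not mirror each other.** Exclusion 4 covers lifetime history, while criterion 5 covers the time since the last visit. This stands to the extent that the two are not a contradiction. It does not explain why the on-study rule is silent on behaviour when 11.9.8 says behaviour is assessed.
- **Listings are no departure from the protocol.** The C-SSRS is not among the safety variables in Protocol 4.2 or SAP 2.2.2, nor in the safety analyses of Protocol 13.4.1. This stands. With few events expected, listings plus AE tables are a defensible minimum, so the added table is an improvement rather than the correction of an error.
- **The affected case may be rare.** Many attempts may come with a Yes to Question 4 or 5. The documents neither reproduce the items nor say that behaviour counts as such an answer, so the frequency cannot be judged from them.
- **Other safeguards exist.** They do, and they limit the point. A reader might infer that on-study suicidal behaviour triggers no required action at all. The AE and SAE reporting duties and the real-time triage rule that out. A reader might infer that only investigator judgement under criterion 7 remains. Criteria 1 and 2 and discretionary item 1 also apply, and criterion 2 does not depend on the site. A reader might infer that suicidality reaches a by-arm table only if it codes to an Appendix 12.2 term. SAP 10.2 tabulates every TEAE and serious TEAE by arm, whatever the term.

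**Conclusion.** Two limited gaps remain. First, suicidal behaviour recorded on study without a Yes to Question 4 or 5 has no specific mandated withdrawal or referral; only the general routes and the reporting duties apply. Second, the systematically collected C-SSRS data, six Treatment Period assessments per completer aged 6 or over, yield no by-arm count, and suicidality is compared between arms only as reported AEs.

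This is a cheap improvement. It does not touch the primary efficacy analysis, and few subjects are likely to be affected, although each case would be serious. That expectation is an assumption, because the documents give no rate. The first gap also assumes that behaviour can be recorded without a Yes to Question 4 or 5, which the documents neither state nor exclude. The second gap needs no such assumption: it follows directly from SAP 10.4.8.

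**What to change.** 1. **Protocol.** The sponsor should reconcile 6.3 criterion 5 with Exclusion 4 and 11.9.8, so that the protocol states in one place how suicidal behaviour recorded on study is handled. The content of that statement is for the sponsor's medical lead; none is proposed here. Cost: one sentence in a protocol amendment.

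2. **SAP 10.4.8.** Before unblinding, replace the statement that no C-SSRS summaries are planned with one by-arm table. It should give the number and percentage of subjects with (a) any ideation after the first dose, (b) ideation at Question 4 or 5, and (c) any suicidal behaviour, all during the Treatment Period, among subjects with at least one post-Baseline C-SSRS. The Treatment Period is the right window for a randomised comparison, because placebo subjects who enter Transition move to LCM (Protocol 7.2.3). Fixing categories and denominator before unblinding keeps them from being chosen with arm data in view. Cost: one descriptive table with few expected events, from data already collected.
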